#### *3.2.2.4. Others*

- Number of patients receiving rescue medication at least once during treatment period
- Patients with at least one Grade 2 or higher non-skin bleeding event during treatment period.

For each endpoint, a patient will be considered to have had an event if the event was observed at least once during the treatment period for rescue medication, and during treatment or follow-up period for bleeding event.

### **3.2.3. Exploratory Endpoints**

#### *3.2.3.1. Peak Platelet Count*

- Peak platelet counts during the treatment period without use of rescue medication

For each patient, peak platelet count is patient's highest platelet count during the treatment period, without use of rescue medication.

#### *3.2.3.2. Bleeding Score*

The ITP bleeding assessment score as described by Page et al. 2007 will be used to characterize bleeding tendency.

Table 3-1 The ITP Bleeding Score Assessment

Site	Bleeding Grade		
	0	1	2
Skin [physical Examination (PE)]	None	1–5 bruises and/or scattered petechiae	>5 bruises with size $>2$ cm and/or diffuse petechiae
Oral (PE)	None	1 blood blister or $>5$ petechiae or gum bleeding that clears easily with rinsing	Multiple blood blisters and/or gum bleeding

Site	Bleeding Grade		
	0	1	2
Skin (Hx)	None	1–5 bruises and/or scattered petechiae	>5 bruises with size >2 cm and/or diffuse petechiae
Oral (Hx)	None	1 blood blister or >5 petechiae and/or gum bleeding <5 min	Multiple blood blisters and/or gum bleeding >5 min
Epistaxis	None	Blood when blowing nose and/or epistaxis <5 min (per episode)	Bleeding >5 min (per episode)
Gastrointestinal	None	Occult blood	Gross blood
Urinary	None	Microscopic (+ve dipstick)	Macroscopic
Gynecological	None (normal period)	Spotting not at time of normal period	Bleeding >spotting not at time of period or very heavy period
Pulmonary	None	N/A	Yes
Intracranial haemorrhage	None	N/A	Yes
Subconjunctival haemorrhage	None	Yes	N/A

- abbreviation: ITP, immune thrombocytopenia; PE, physical examination; N/A, not applicable
- Note: In case of a breakthrough bleeding, the patients will discontinue the trial.

### 3.2.3.3. *Quality of Life as Measured by the SF-36 Score*

The Short Form (36) Health Survey is a 36-item, patient-reported survey of patient health. The SF-36 is a measure of health status and the survey will be conducted according to the SF-36 quality of life questionnaire Version 2.0.

The assessments will be performed at time points indicated in Schedule of Events ([Appendix 15.1](#)).

### 3.3. Dose Interruption and Reduction

It is recognized that some AEs may require dose adjustment or study drug discontinuation. Intra-patient dose reduction or escalation is permitted and based upon treatment-related adverse events observed. Guidelines for dose interruption or reduction are specified in Protocol Section 3.1.1.

After experiencing an AE, patients whose laboratory results return to baseline values and remain stable for 4 consecutive weeks have the option to increase the dose of SKI-O-703 1 dose level up to the randomized dose level.

## 4. General Statistical Considerations

### 4.1. Reporting Convention

Continuous variables (quantitative endpoints) will be summarized using the mean, the standard deviation (SD), median, range (minimum value and maximum value), and interquartile. Categorical variables (qualitative endpoints) will be summarized using frequency counts (number) and percentages, unless otherwise specified.

For the summary statistics of all numerical variables unless otherwise specified, minimum and maximum will be displayed to the same level of precision as reported. Mean, median and interquartile will be displayed to one level of precision greater than the data collected. Standard deviation / standard error will be displayed to two levels of precision greater than the data collected. All percentages will be rounded to one decimal place. If the percentage is 100, no decimal is required.

P-values will be rounded to three decimal places. If a p-value is less than 0.001 it will be reported as “<0.001.” If a p-value is greater than 0.999 it will be reported as “>0.999.”

All statistical tests will be 2-sided using a 5% significance levels, leading to 95% (2-sided) confidence intervals (CIs). This will be used for each pairwise comparison with placebo, i.e., there will be no adjustments for multiplicity since this is a Phase 2 study, and interim analysis will only be performed on safety and PK analysis.

Patients will be identified in the listing by the subject identifier. Data will be displayed in all listings sorted by treatment group.

### 4.2. Baseline Definition and Study Day

For platelet count related endpoints, baseline will be defined as the lowest platelet count within 1 month prior to or on the date that the first dose of study drug (SKI-O-703 or placebo) is taken. Data from Central lab will be used first. Otherwise, baseline will be defined as the last non-missing evaluation prior to or on the date that the first dose of study drug (SKI-O-703 or placebo) is taken.

The study day will be calculated as:

- Study day = assessment date - first dose of study drug (SKI-O-703 or placebo) date + 1, if assessment date is on or after the first dose date.
- Study day = assessment date – first dose of study drug (SKI-O-703 or placebo) date, if assessment date is prior to the first dose date.

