7.1 Primary Endpoint - Platelet Response

- Patient platelet response is defined as platelet count $\geq 30,000/\mu\text{L}$ and doubling the baseline (average of 2 previous counts), at any visit during the treatment period and without the use of rescue medication

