7.2.2 Change from Baseline in Platelet Counts

- Change from baseline in the average of the last 2 platelet counts during the treatment period

For each subject, the change from baseline in the mean of the last 2 platelet counts during the treatment period will be calculated. For those subjects with only 1 platelet count during treatment period, the change from baseline in the single platelet count will be used.

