7.7.3 Analysis of Platelet Response

The primary efficacy endpoint will be summarized as overall platelet response rate (ORR) by treatment group and analyzed using Fisher's exact test to compare the difference in ORR between each active treatment group and placebo. A logistic regression model will also be performed on platelet response and include treatment, baseline platelet count and prior TPO-receptor agonist use, provided there are enough subjects in each subgroup. The odds ratio for the treatment effect compared to placebo (together with 95% CI and p-value) will be provided.

Summary statistics will be provided on the number (%) of subjects achieving platelet response by each treatment group and the combined active treatment group. Fisher's exact test on the differences in the ORR will therefore be provided for:

- Each active treatment group (200 mg BID, 400 mg BID) vs. placebo
- Combine active treatment groups vs. placebo
- 200 mg BID vs. 400 mg BID.

Furthermore, summary statistics will be provided on the number (%) of subjects achieving platelet response by each treatment group and the subgroups defined in [Section 7.6](#).

A subject will be classified as a platelet responder if subject shows at least 1 platelet count $\geq 30,000/\mu\text{L}$ and doubling the baseline (average of 2 previous counts), at any visit during treatment period, without use of rescue medication. The ITT analysis set will be used in the analysis of the primary endpoint.

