## 3.2. Study Endpoints

### 3.2.1. Primary Endpoint

The primary endpoint, patient platelet response, is defined as platelet count  $\geq 30,000/\mu\text{L}$  and doubling the baseline (average of 2 previous counts), at any visit during the treatment period and without the use of rescue medication. Refer baseline definition to Section 4.2.

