### 8.1. Primary Efficacy Endpoint

The primary efficacy endpoint, patient platelet response, is defined as platelet count  $\geq$  30,000/ $\mu$ L and doubling the baseline (average of 2 previous counts), at any visit during the treatment period and without a use of rescue medication. Refer baseline definition to Section 4.2. The average based on last 2 platelet counts at the time of evaluation.

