#### 8.1.1. Primary Analysis

The platelet responses after using rescue medication during treatment period will be set to missing and will be imputed as the average of the last 2 previous non-missing platelet counts. For example, if platelet count in Week 2 Day 8, Week 3 and Week 5 are 45,000, missing, and 48,000 respectively, the average will be calculated by results from Week 2 Day 8 and Week 5.

The primary efficacy endpoint will be summarized as overall platelet response rate (ORR) with exact unconditional 95% confidence intervals (CI) by treatment group. The ORR difference and exact unconditional 95% CI will be provided between each of active treatment groups and placebo group, and between two active treatment groups. The p-value from Fisher's exact test will be presented.

For patients whose ORR cannot be adequately determined, their ORR will be imputed using a non-responder imputation (NRI) approach.

Summary statistics will be provided on the number (%) of patients achieving platelet response by each treatment and the combined active treatment groups. The differences in the ORR, 95% CI and p-value from a Fisher's exact test will therefore be provided for:

- Each active treatment group (200 mg BID, 400 mg BID) vs. placebo
- Combine active treatment groups vs. placebo
- 200 mg BID vs. 400 mg BID.

A logistic regression model will also be performed on platelet response as dependent variable and treatment group, baseline platelet count and prior TPO-receptor agonist use as covariates. The odds ratio for the treatment effect compared to placebo (together with 95% CI and p-value) will be provided.

Bar plots on difference in proportions of ORR and exact unconditional 95% CI will be provided by treatment group and combined active treatment group.

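### The SAP does not apply the protocol's primary endpoint rule: it changes the baseline, appears to change single counts to two-count averages, and declares neither as a departure

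*SAP*

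**What the plan says.** **Protocol.** Section 7.1 requires a count of at least 30,000/µL and "doubling the baseline (average of 2 previous counts), at any visit during the treatment period", without rescue medication. Section 7.7.3 makes one count sufficient: "A subject will be classified as a platelet responder if subject shows at least 1 platelet count" meeting both conditions. The protocol averages on-treatment counts only for a secondary endpoint, in Section 7.2.2, where "the change from baseline in the mean of the last 2 platelet counts during the treatment period will be calculated". Section 7.2.3 dates response at the first visit with a count of at least 30,000/µL.

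**SAP.** Section 3.2.1 repeats the protocol's endpoint and adds "Refer baseline definition to Section 4.2". Section 8.1 does the same. In Section 4.2, for platelet endpoints, "baseline will be defined as the lowest platelet count within 1 month prior to or on the date" of first dose. Section 8.1 then adds "The average based on last 2 platelet counts at the time of evaluation", without saying what this average is for. Under Section 8.1.1, responses after rescue "will be set to missing and will be imputed as the average of the last 2 previous non-missing platelet counts". The example that follows has a missing Week 3 and states that "the average will be calculated by results from Week 2 Day 8 and Week 5". Section 3.2.2.3 keeps the protocol's first-visit dating, but Section 8.2.3 describes the Kaplan-Meier curve as using the later visit that meets the criteria. Section 12 lists the edits to 4.2, 8.1.1 and 8.2.3 as changes from SAP v0.2.

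**The concern.** The lowest count in a month is not the average of two counts, yet both stand in the SAP's definition of the same endpoint. The cross-reference to Section 4.2 does not settle the matter, because the averaged-baseline wording stays in the sentence before it. It is also unclear whether an on-treatment value is a single count, as the protocol says, or an average of two.

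Platelet response is the only primary efficacy endpoint. The same classification feeds the Fisher tests, the logistic model, the subgroup tables and time to response. The placebo arm has 12 patients, so one patient is 1/12 = 8.3 percentage points.

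**Working it through.** **The plan's own figure.** Inputs from Protocol 7.4: 24 active, 12 placebo, 50% vs 1%, two-sided 5%. Pooled rate = (24×0.50 + 12×0.01)/36 = 0.3367. Null SE = √[0.3367×0.6633×(1/24+1/12)] = 0.1671. Alternative SE = √(0.25/24 + 0.0099/12) = 0.1060. Continuity correction = (1/24+1/12)/2 = 0.0625. Power = Φ[(0.49 − 0.0625 − 1.96×0.1671)/0.1060] = Φ(0.943) = 82.7%. This matches the stated figure. It takes response rates as inputs, so the definition does not alter it.

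**Effect of the baseline rule.** Threshold = max(30k, 2 × baseline), in thousands per µL. Take two pre-dose counts from the same window, both below 30k as the entry criteria require.

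| Pre-dose counts | Average rule | Lowest-count rule |
|---|---|---|
| 12k, 16k | max(30, 28) = 30k | max(30, 24) = 30k |
| 16k, 28k | max(30, 44) = 44k | max(30, 32) = 32k |
| 15k, 29k | max(30, 44) = 44k | max(30, 30) = 30k |

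Over all whole-thousand pairs from 1k to 29k the lowest-count threshold is never higher. The largest gap is 14k (15k and 29k), and it approaches 15k as the upper count nears 30k. The thresholds differ whenever the mean exceeds 15k and the counts differ.

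This ordering needs both counts to come from the SAP's one-month window. Protocol 4.1.1 requires only the confirmatory count to fall in Screening, and the protocol does not name the two counts to be averaged. With 12k from before the window and 28k throughout it, the average rule gives 2 × 20 = 40k and the lowest-in-window rule gives 2 × 28 = 56k.

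**Effect of averaging on-treatment counts.** If the mean of two counts reaches a threshold, the larger count does too. Against a fixed baseline, averaging can only remove responders.

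**Both together, pre-dose 16k and 28k.**
- On-treatment 20k, 40k, 22k. Protocol: 40 < 44, non-responder. Lowest baseline, single count: 40 ≥ 32, responder. Lowest baseline, averaged: best mean (40+22)/2 = 31 < 32, non-responder.
- On-treatment 16k, 46k, 16k. Protocol: 46 ≥ 44, responder. Lowest baseline, averaged: (16+46)/2 = 31 < 32, non-responder.

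Patients can therefore change class in either direction.

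**What one patient is worth.** Fisher's exact test, two-sided p < 0.05, 24 vs 12:

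| Placebo responders | Fewest active responders needed | One fewer |
|---|---|---|
| 0/12 | 8/24 (p = 0.033) | 7/24 (p = 0.070) |
| 1/12 | 11/24 (p = 0.031) | 10/24 (p = 0.059) |
| 2/12 | 13/24 (p = 0.040) | 12/24 (p = 0.076) |

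**Dating.** SAP 8.2.3 (later visit) disagrees with SAP 3.2.2.3 and Protocol 7.2.3 (first visit). The dating sentences in those two sections have a gap of their own. They ask only for a count of at least 30,000/µL and omit doubling, under an endpoint title that says more than 30,000/µL and twice baseline.

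**The case against.** The best defence is that the SAP's additions form one rule. The average in 8.1 is the on-treatment value, the 8.1.1 example shows how to pair counts around a missing visit, the later visit is the natural date for a two-visit average, and 4.2 supplies the baseline. Much of this stands: these are better read as one averaged-count rule than as separate errors. But that rule is not the protocol's endpoint, and it conflicts with SAP 3.2.2.3 and with the averaged-baseline wording retained in 3.2.1 and 8.1.

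It can also be said that Protocol 7.7 leaves methods and data conventions to the SAP, and that Section 12 discloses the edits. They are disclosed, but as additions to an earlier SAP, not as departures from the protocol. Replacing the reference value and the unit of judgement goes beyond a data convention.

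A third argument is that either rule applies equally to blinded arms and the effect may be small. An illustrative simulation supports this in part. It assumed log-normal counts, within-patient CV 20% to 30%, between-patient CV 40%, median 15k or 18k, eight visits and 50% active response; the variability and medians are not in the documents. Against an active-minus-placebo difference of 40.5 to 49.5 points, the lowest baseline with single counts moved the difference by −2.0 to +2.2 points. With averaged counts it moved by −1.5 to −4.2 points, at most about one active patient in 24. The conclusion does not rest on these figures.

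Two stronger readings are tempting. A reader might infer that a high post-rescue count could enter an average and create a response. The documents do not support this: SAP 8.1.1 sets post-rescue results to missing and imputes from previous non-missing counts. Under a single-count rule, a mean of two pre-rescue counts cannot exceed the larger of them. The Week 5 value in the example is later than the missing visit, and Section 12 calls that edit the missing-visit scenario, so it is a misplaced illustration. A reader might also infer that the SAP favours the drug or costs power. Neither follows, because the two changes pull in opposite directions in every arm.

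**Conclusion.** The concern holds. On its most coherent reading (a two-count on-treatment average against the lowest baseline, dated at the later visit), the SAP analyses a different primary endpoint from the protocol's. It does so while still printing the protocol's wording and without declaring the change.

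For counts from the same window the baseline rule lowers the threshold by 0 to just under 15,000/µL, and on-treatment averaging tightens the rule. The net effect on the response rates and on the treatment difference is not fixed. The threshold and Fisher results are exact. How often patients would be reclassified cannot be known from the documents. Because one placebo patient moves the cut-off by two or three active responders, the rule should be settled before unblinding.

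**What to change.** Before database lock and unblinding:

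1. **SAP 4.2.** For platelet response and time to response, use one pre-dose baseline equal to the mean of two named counts, as in the protocol. Give the laboratory source and a rule for when only one count exists. State which baseline applies to the other platelet endpoints, the model covariate and the 15,000/µL subgroup.
2. **SAP 8.1 and 8.1.1.** State that each on-treatment count is judged singly, as in Protocol 7.7.3. Delete the sentence on the last two counts, or limit it to a named use.
3. **SAP 8.1.1.** Move the Week 2 Day 8 and Week 5 example out of the post-rescue rule, or delete it.
4. **SAP 8.2.3 and 3.2.2.3.** Date response at the first visit that meets the full primary criterion: at least 30,000/µL, doubling of baseline, no rescue. Correct 3.2.2.3, whose dating sentence omits doubling and whose endpoint title says more than 30,000/µL.
5. **Alternatives.** Report a lowest-baseline or averaged-count version only as a labelled sensitivity analysis. If the sponsor keeps it as primary, declare it in SAP 12 as a change from the protocol and report the protocol definition alongside.

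The cost is SAP wording and derivation code. Response rates may move up or down, depending on what would otherwise have been programmed.

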6.4.3 Electrocardiograms

For all subjects, single ECG (predose) will be obtained, after the subject has been in the supine position for at least 5 minutes, on the first day of dosing and on Day 1 of each subsequent week at the time points indicated in the schedule of events ([Table 2](#)). For subjects in the safety run-in subsets and PK/PD subset subjects who are in safety run-in subset only, ECGs will be obtained on the first day of dosing at predose, 1, 2, 4, 8, and 12 hours (± 10 min) after the study drug administration. Electrocardiogram assessments will include comments on the rhythm; presence of arrhythmia or conduction defects; morphology; or ST segment, T wave, and U wave abnormalities; as well as whether the tracings are normal or abnormal and if there is any evidence of myocardial infarction. In addition, the following parameters will be measured and reported: RR interval, PR interval, QRS width, QT interval, and QTcF.

The investigator will determine whether any of the ECG results are normal or abnormal and whether any abnormal results are clinically significant or not clinically significant. Clinical significance is defined as any variation in results that has medical relevance and may result in an alteration in medical care (eg, active observation, diagnostic measures, or therapeutic measures). If a clinically significant change from screening is noted, the clinically significant value and the reason for clinical significance will be documented on the AE page of the subject's eCRF. The investigator will continue to monitor the subject with additional assessments until the values have reached either the reference range or the values at Screening or until the investigator determines that follow-up is no longer medically necessary.

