## **9.6. Electrocardiogram**

Electrocardiogram (ECG) assessments will include comments on the rhythm; presence of arrhythmia or conduction defects; morphology; or ST segment, T wave, and U wave abnormalities; as well as whether the tracings are normal or abnormal and if there is any evidence of myocardial infarction. In addition, the following parameters will be measured and reported: RR interval, PR interval, QRS width, QT interval, and QTcF.

The investigator will determine whether any of the ECG results are normal or abnormal and whether any abnormal results are clinically significant or not clinically significant. Clinical significance is defined as any variation in results that has medical relevance and may result in an alteration in medical care (eg, active observation, diagnostic measures, or therapeutic measures).

Summary tables will be presented for ECG data and change from baseline by treatment group and combined active treatment group. The ECG investigator interpretations will be summarized in shift tables comparing the ECG value interpretation categories of each post-baseline visit with the value at the baseline visit. In addition, the worst post-baseline ECG value will be compared with the value at the baseline visit (with worst of all being Abnormal Clinically Significant and best being Normal).

ECG data by patient and ECG parameter will be presented in a listing.

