## **11. Pharmacodynamics**

### **11.1. Pharmacodynamic Data Handling**

Subjects with baseline CD63+ values below the limit of detection will be defined as low responders and excluded from the PD set and all summaries of PD data. Baseline will be defined as the percentage of activated CD63+ cells at predose samples on Day 1.

All PD data will be rounded to 3 significant figures for reporting purposes. The only exceptions will be actual sampling times and  $TE_{max}$  (which will be rounded to 2 decimal places). Summary statistics will be rounded to the same precision as individual data, with the exception of n (which will be reported as an integer).

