- \* Patients in the safety run-in period will have clinic visit on Week 2/Day 8 ( $\pm 2$  days) for the mentioned assessments including hematology (differential) tests. For other patients, this visit will be laboratory only visit to perform hematology (differential) tests only.
- a Clinic / laboratory visit windows are about  $\pm 3$  days for all dosing period and laboratory visits and about  $\pm 1$  week for clinic follow-up visits. The W12/D84 (EOT) visit should be performed while on therapy.
- b Complete physical examination at Screening and abbreviated physical examination at other visits.
- c For all patients: ECG on the first day of dosing and on Day 1 of each subsequent week as specified in the table above. For patients in the safety run-in only: ECG on the first day of dosing at 1, 2, 4, 8, and 12 hours after the study drug administration.
- d For women of childbearing potential only: Serum pregnancy tests are performed at Screening. FSH testing is needed for post-menopausal female patients only.
- e Laboratory only visits will be performed on Day 4 (Week 1) for all patients and on Week 2/Day 8 ( $\pm 2$  days) for patients other than those enrolled in the safety run-in period.
- f Study drug dispensing and administration can occur at unscheduled visit.
- g Samples to be collected as follows:
  - For the patients in the safety run-in period only (for PK only; no PD assessments):
    - Day 1: morning predose, 0.25, 0.5, 1, 2, 4, 8, and 12 hours (evening predose).
    - Day 8 ( $\pm 2$  days): morning predose, 0.25, 0.5, 1, 2, 4, 8, and 12 hours (evening predose).
    - Week 12: morning predose, 0.25, 0.5, 1, 2, 4, 8, and 12 hours.
  - For the patients in the PK/PD subset only (for PK/PD):
    - Day 1: morning predose, 0.25, 0.5, 1, 2, 4, 8, and 12 hours (evening predose).
    - Week 12: morning predose, 0.25, 0.5, 1, 2, 4, 8, and 12 hours.
  - For other patients not included in the safety run-in period or PK/PD subset (for PK only):
    - Week 12: morning predose.
- h Only on Day 1 (Week 1).
- i Bleeding score assessment as described by [Page](#) et al 2007 should be performed on Day 1 of each week specified in the above table and at follow-up visit.
- j A blood sample for genotyping will be drawn at baseline (Day 1, before dosing) from patients who have consented to participate in the genetic analysis component of the study.

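### The date-only baseline rule in SAP 4.2, read as written, makes the 12-hour post-dose ECG the baseline for the five safety run-in subjects

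*SAP*

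**What the plan says.** SAP 4.2 gives platelet counts their own baseline and then sets a general rule: "baseline will be defined as the last non-missing evaluation prior to or on the date that the first dose of study drug" is taken. It refers to a date and never to a dosing time.

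Protocol 6.4.3 schedules one Day 1 tracing for everyone ("For all subjects, single ECG (predose) will be obtained") and a series for the run-in subjects: "ECGs will be obtained on the first day of dosing at predose, 1, 2, 4, 8, and 12 hours". SAP Table 15-1 footnote c describes the run-in series without the predose recording ("For patients in the safety run-in only: ECG on the first day of dosing at 1, 2, 4, 8, and 12 hours"). It also omits the word predose for all other patients, although the matching protocol footnote includes it.

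SAP 9.6 relies on the general rule: "Summary tables will be presented for ECG data and change from baseline by treatment group and combined active treatment group". It also plans shift tables of the investigator's interpretation, by visit and for the worst post-baseline value, against the baseline visit. It neither defines an ECG baseline nor says which tracing to use when a visit has several. SAP 9.3 and 9.4 do give multiple-value rules for laboratory tests and vital signs.

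Pharmacodynamics is handled differently. SAP 11.1 fixes that baseline as the percentage of activated CD63+ "cells at predose samples on Day 1".

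**The concern.** A change from baseline measures a drug effect only if the baseline precedes the drug. On Day 1 the run-in subjects have six ECGs on one calendar date, five of them after dosing, and a rule that takes the last value on that date takes a post-dose one.

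This matters more than five subjects would suggest. Routine on-treatment ECGs are predose under Protocol 6.4.3, so the run-in Day 1 series is the only scheduled look at ECGs after a dose. Protocol 3.1.2 creates the run-in because 400 mg BID had not been studied, and Protocol 1.5 counts cardiovascular effects among the important potential risks. Protocol 1.3 reports that food delayed median Tmax by 2.5 to 4 hours, and dosing is with food. The tracings nearest peak exposure are therefore likely to be among those that fall before the 12-hour baseline.

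**Working it through.** There is no figure in the plan to reproduce here; the check applies the stated rule to the stated schedule.

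**Inputs**
- General baseline rule: last non-missing value up to and including the date of first dose (SAP 4.2).
- Run-in ECG times on Day 1: 0 (predose), 1, 2, 4, 8 and 12 hours, with a 10-minute window (Protocol 6.4.3).
- The first dose is the Day 1 morning dose (Protocol 5.2).
- Run-in subjects: 2 at 400 mg BID, 2 at 200 mg BID, 1 on placebo (Protocol 3.1.2).
- Planned arm sizes: 24, 24 and 12 (Protocol 3.1).

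**Step 1: which ECG is selected.** The 12-hour tracing falls on the dosing date if dose time + 12 h + 10 min is before midnight, that is, for a dose before 11:50. Dose times from 07:00 to 11:30 all give the 12-hour ECG. A dose at 12:00 gives the 8-hour ECG, which is still post-dose. No morning dose leads the rule to the predose recording if the scheduled series is complete.

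**Step 2: what follows for these subjects.** Let Q0 be the predose QTcF, Q12 the 12-hour value, Qv a later value, and d = Q12 − Q0.
- Change at 12 hours: Q12 − Q12 = 0, whatever the drug did.
- Change at a later visit: Qv − Q12 = (Qv − Q0) − d. The reported change is the change from predose less d.
- The 1, 2, 4 and 8 hour tracings come before the selected baseline. They are not post-baseline values, so they can be left out of the worst-value comparison in SAP 9.6. This needs no assumption about d.
- In the interpretation shift tables, the category of the 12-hour tracing becomes the comparator.

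**Step 3: reach.** 2/24 = 8.3% of each active arm, 1/12 = 8.3% of placebo, and 5/60 = 8.3% overall.

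**Step 4: size.** The documents do not give d. As an assumption, take a peak effect of 5 to 20 ms with 0 to 100% of it remaining at 12 hours. The shift in an active-arm mean is −d × 2/24.

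| Assumed peak (ms) | Share left at 12 h | Shift per affected subject (ms) | Shift in active-arm mean (ms) |
|---|---|---|---|
| any | 0% | 0 | 0 |
| 5 | 100% | −5 | −0.42 |
| 10 | 50% | −5 | −0.42 |
| 20 | 50% | −10 | −0.83 |
| 20 | 100% | −20 | −1.67 |

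**Step 5: other measures under the same rule.** Vital signs, laboratory tests, SF-36 and bleeding score have no scheduled post-dose repeat on Day 1, and subjects outside the run-in have only the predose Day 1 ECG. With a predose cut-off, the run-in baseline becomes the Day 1 predose ECG, the 1 to 12 hour tracings become post-baseline, and the shift is 0 ms.

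**The case against.** The strongest reply is that predose intent is already visible. SAP 3.1 and Protocol 3.1 list the ECG among the Day 1 baseline safety evaluations and describe randomization and dosing afterwards. Protocol 5.2 puts visit-day procedures before the morning dose, and SAP 9.6 refers to the baseline visit. A programmer may well choose the predose tracing, and all ECG data are listed by patient, so the values remain visible. This shows intent, but it does not override the operative definition in SAP 4.2. For run-in subjects the baseline visit itself holds six tracings, with no rule for choosing among them.

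Several objections to stronger readings do stand:
- **That the rule spoils every non-platelet baseline.** It does not. Pharmacodynamics has its own predose definition, and among scheduled assessments only the run-in ECGs are repeated after dosing on Day 1. An unscheduled post-dose value could be caught, since SAP 9.4 lets unscheduled visits into the vital-sign baseline, but none is planned.
- **That the QTcF effect is subtracted out.** Only what is still present at 12 hours, just before the next dose, is removed. An effect that peaks earlier or builds up over 12 weeks is not fully removed, and d may be zero or negative.
- **That shift tables are lowered by d ms.** They use interpretation categories, not milliseconds.
- **That the 30 ms QTcF criterion in Protocol Table 1 would be missed.** Investigators apply it during treatment. The SAP does not apply it, and SAP 9.6 has no such category.
- **That the decision to resume enrolment is affected.** The DMC review falls under a separate interim SAP that is not available here, so its baseline rule cannot be checked.

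A strict date-and-time rule also has a cost. SF-36 and bleeding score are first collected on Day 1, and without recorded times they could lose their baseline. The fix needs a fallback.

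**Conclusion.** The point holds for the run-in ECGs. The SAP states a rule which, followed literally, gives a post-dose ECG baseline for 5 of 60 planned subjects. The consequences that need no assumed effect are the zero change at 12 hours, the possible loss of the 1 to 8 hour tracings from the worst-value comparison, and the wrong shift-table comparator. The understatement of later QTcF changes depends on the effect remaining at 12 hours. Over an assumed 0 to 20 ms, it is 0 to 20 ms in an affected active-arm subject and at most about 1.7 ms in an active-arm mean.

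Arm-level ECG summaries are therefore little disturbed. The damage is to individual changes and to the only scheduled post-dose ECG series. These figures assume a complete series, a morning dose, the planned 2:2:1 run-in allocation and the planned arm sizes. The correction is worth making before database lock, because the SAP exists to fix such choices in advance.

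**What to change.** 1. In SAP 9.6, state that the ECG baseline is the Day 1 predose recording, or the last earlier ECG if that one is missing, and that the Day 1 tracings at 1 to 12 hours are post-baseline time points.
2. In SAP 4.2, change the general rule to the last non-missing evaluation before the first dose. Use date and time where times are recorded. Where no time is recorded, as may be the case for SF-36 and bleeding score, treat Day 1 assessments scheduled before dosing as predose.
3. In SAP Table 15-1 footnote c, restore the predose wording for all patients and for the run-in series, to match the protocol footnote.

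The cost is a few sentences in the SAP and a small programming check on recorded times. The predose ECG is already scheduled for every subject, so no new data are needed.
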